#### **2. Oral Glucose Tolerance Test (OGTT)**

**Description:** An OGTT will be performed with multiple blood draws over 3 hours. The purpose of the OGTT is to provide a controlled oral stimulus to effect changes in lipolysis and hepatic glucose release.

**Risk:** The subjects rarely experience nausea within 15 min of consuming the drink, however, the amount of carbohydrate is very similar to a large soda, which is regularly consumed by this patient population.  
**Justification/Minimization:** A standard oral challenge is needed to study insulin resistance in order to examine the relationship with sleep. Our team of investigators, CTRC pediatric research nursing staff and physicians are well experienced with the OGTT blood draw procedure. A floor nurse located on the 9th floor of CHC will be available during our inpatient visits and patients will be distracted by TV or other similar means during the OGTT, to minimize queasiness.

### 3: Actigraphy

**Description:** Each subject will wear an accelerometer for 14 days (Spectrum, by Philips Resperonics) to measure habitual sleep/wake patterns. The accelerometer will be worn on the non-dominant wrist, similar to a wristwatch.

**Risk:** There is no risk involved with the actigraphy device.

**Justification/Minimization:** Actigraphy is an effective tool for the objective measurement of sleep because they have the ability to continuously record sleep and activity data and such data can be used to estimate sleep/wake patterns. They provide more detailed information than pedometers, which only measure walking steps, and help get around the recall bias of questionnaires. We are currently using the Spectrum Actigraphy watches in adolescents in our other research studies and in routine clinical care; therefore, we are familiar with their use in this population and have the necessary computer software and interpretation skills.

### 4. Questionnaires

**Description:** Participants will complete questionnaires regarding their sleep, physical activity and eating habits, and mood and behavior.

**Risk:** There is a small possibility that participants will be uncomfortable answering a particular question.

**Justification/Minimization:** The questionnaires used in the study are widely used in both research and clinical practice, and are not of a particularly sensitive nature. Participants will be able to skip any items that they find uncomfortable. None of the items assess for suicidality.

### 5. Overnight stay with salivary melatonin sampling

**Description:** Saliva will be collected every 30-60 minutes from 5pm-noon.

**Risks:** Discomforts include unsettling to sleep away from home in a strange place. Providing saliva samples may make the mouth feel dry. Participants may obtain inadequate sleep.

**Justification:** The melatonin will provide data on the chemical signaling involved in falling asleep and waking up, as they relate to changes seen with the sleep study. Saliva is good alternative to blood sampling in pediatric populations. Short term risks are associated with inadequate sleep, including daytime sleepiness and inattention. Inadequate sleep is readily reversed with 1-2 nights of good sleep. As will be indicated on the consent form, subjects will be asked not to drive, operate heavy machinery, or engage in jobs that require a high degree of coordination, balance, or attention (e.g., roofing) for the day subsequent to the overnight visit. When reviewing the consent form, we will call attention to these prohibitions and exclude participation if they report being unable to follow them (e.g., the participant has a job that requires driving).

### 6. Violation of Privacy and Loss of Confidentiality

**Description:** These are both risks to which research participants are exposed. The possibility of these risks increases when protected health information is collected. Every effort will be made to decrease this risk by limiting access to protected health information, storing this information in a password protected database, and identifying subjects only by a unique identifier that is kept in a separate location in a locked container, traceable only by study personnel. All of the tests involve the risk of identifying asymptomatic abnormalities. The study may include risks that are unknown at this time.

**Justification/Minimization:** Every effort will be made to decrease the risk of loss of confidentiality by limiting access to protected health information, storing this information in a password protected database, and de-identifying study specimens.

## **Data Analysis Plan:**

**Aim 1 Analysis Plan:** Demographic and clinical characteristics will be summarized by group with descriptive statistics. Prior to analysis, variables will be examined for unusual values for query, missing data, and whether distributions are non-normal, in which case a transformation may be applied.

**Melatonin modeling:** The timing of melatonin onset and offset will be computed according to standard procedures that have been validated in adolescents . We will define DLMO phase as the clock time

at which evening salivary melatonin concentrations increase and remain above a 4pg/mL threshold using linear interpolation between successive samples . Similarly, we will define DLMOff phase as the clock time at which salivary melatonin concentrations fall below this threshold. Phase angles of entrainment will be computed as the time interval between DLMO and average actigraphic estimates of sleep variables, including bedtime, mid-sleep time, and wake time. Additional characterization of the melatonin profile, including assessment of melatonin amplitude, will also be conducted.

Aim 2 Data Modeling Plan: To investigate the relationship between sleep/wake behavior and circadian phase in obese adolescents, we will develop a physiologically-based mathematical model of sleep/wake and circadian interactions that simulates adolescent sleep patterns. Model equations will be implemented in MATLAB and solved numerically using an appropriate solver. Initially, we will fit model behavior to published characterizations of adolescent sleep/wake behavior. After establishing a representative model of adolescent sleep, we will assess the role of key model parameters in the production of key elements of adolescent sleep, and we will investigate the role of these parameters in inter-individual differences observed in sleep/wake behavior in study participants as characterized by actigraphy data.

Aim 3 Calculations and Data Analysis Plan:

*Power calculation:* A sample size of 30 participants will provide 80% power to detect a correlation coefficient equal to 0.47, given a 2-sided  $\alpha=0.05$ . Because this is a pilot study, even if the null hypothesis is not rejected, the information gained regarding possible effect sizes will be useful in obtaining subsequent extramural funding for additional participants and in planning a larger study.

*Calculation of insulin resistance:* IR will be calculated with the Matsuda Index, a composite model for insulin sensitivity which accounts for changes in both the insulin and glucose concentrations over time . The value derived from this equation is an M value of glucose uptake in mg/m^2/min, which is approximated to results that would likely have been obtained if a more invasive hyperinsulinemic-euglycemic clamp test had been performed . The range of values is 0–14, with 14 being the highest level of insulin sensitivity and zero the lowest. Additional exploratory measures including B-cell function [insulinogenic index ( $\Delta I30/\Delta G30$ ) and ( $\Delta C30/\Delta G30$ ) and disposition index ( $1/I\text{Fasting} \times \Delta I30/\Delta G30$ ) and ( $1/C\text{Fasting} \times \Delta C30/\Delta G30$ ) will also be calculated .

*Relationship between circadian phase and IR:* DLMO and DLMOff will be determined from the measures of salivary melatonin concentrations as described above. Each subject will have one DLMO time and one DLMOff time. The relationship between DLMO and DLMOff and IR will be assessed by comparing DLMO and DLMOff to the whole body Matsuda index using correlation and linear models. All models will have melatonin onset or offset as the outcome, and gender effects will be considered. The relationship between average actigraphy-estimated sleep duration (from sleep watch) and IR will also be tested using correlation and linear models.

3. Roenneberg T. Munich Chronotype Questionnaire. n.d.; <http://www.imp.med.uni-muenchen.de/index.html>. Accessed February 18, 2015.

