**viii. Description of Population to be Enrolled:**

Participants: This pilot study would allow for preliminary data collection on up to 30 obese adolescents (15 male, 15 female).

Recruitment: Participants will be recruited from adolescent, obesity and community clinics.

Subject Criteria:

*Inclusion criteria:*

- 1) High school students between the age of 15-19 years (the peak developmental period for delayed circadian phase);
- 2) BMI >90th percentile for age and sex;
- 3) Tanner stage 2 or greater.

*Exclusion criteria:*

- 1) Any medications that affect IR or sleep (e.g., metformin, hormonal contraception, stimulants, atypical antipsychotics);
- 2) regular use of melatonin or other sleep aids;
- 3) a prior diagnosis of obstructive sleep apnea, diabetes (HbA1c > 6.5), liver disease other than non-alcoholic fatty liver disease, pregnancy or breastfeeding;
- 4) IQ<70 or severe mental illness that may impact sleep (e.g., schizophrenia, psychotic episodes), verified through chart review;
- 5) teens not enrolled in a traditional high school academic program (e.g., home school students);
- 6) night shift employment;
- 7) travel across more than two time zones in the month prior to the study.

Informed Consent Plan: Appropriately qualified and informed personnel who have completed the COMIRB and HIPPA course requirements will fully explain the study protocol and consent form to the subject and guardian verbally in the language they understand. The explanation will be conducted in a quiet environment with adequate time given for the subject and guardian to review the study procedure before the commencement of the study. Asking the subject to explain the study in their own words will assess the subject's understanding. If non-English speaking subjects are enrolled in the study, the investigators will adhere to Section 10C of the COMIRB Instructions for Clinical Investigators regarding the consent of these subjects. The qualified personnel mentioned above will then obtain written consent from the guardian and assent from the subject, co-signed on the consent form, or in subjects who are 18 years or older, direct consent. The PI will make a good faith effort to obtain both parent signatures. The subject and guardian will be provided a copy of the consent form for better understanding and record purposes.

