### **Study Design and Research Methods**

Study Timeline: Participants will have 3 visits: an initial visit, a screening visit, and an overnight study visit. The initial visit will include informed consent and assent and receiving an actigraphy watch and instructions. The screening visit will include questionnaires, 3-hour frequently sampled oral glucose tolerance test (OGTT), and fasting labs to check for other components of metabolic syndrome. During the overnight study visit subjects will be admitted to the Children's Hospital Clinical research center inpatient unit from 4PM Thursday or Friday to 12PM the following day for salivary melatonin collection. During the entire protocol, teens will be asked to abstain from caffeine, non-steroidal anti-inflammatory drugs, marijuana, high carbohydrate meals, and alcohol.

Initial visit and sleep/wake monitoring: The initial visit will last approximately 30 minutes and will include consent and assent. Participants will be provided an actigraphy watch to monitor typical home sleep patterns. The Spectrum sleep/wake monitor (Phillips Resperonics, Bend, OR) will be worn on the non-dominant wrist and will collect data on movements in 1-min bins. The watch will be worn for the 7 days preceding the initial visit and participants will complete a concurrent sleep diary emailed to them each morning via RedCap to allow for removal of artifacts (e.g., failure to wear the actigraphy watch during a portion of the night). If participants have not completed the sleep diary by mid-morning, a RedCap email and text message reminder will be sent. The text messages will be generic so as not to identify the participant or that they are part of a research study. If participants do not have email or computer access, they can complete a paper/pencil sleep diary.

Screening visit and sleep/wake monitoring: The screening visit will last approximately 4 hours and will ideally occur on Thursdays or Fridays in order to be consistent with the amount of accumulated sleep debt incurred over the week. Menstruating girls will be scheduled in the follicular phase when possible, as menstrual timing can influence measures of IR. Participants will receive or be mailed an actigraphy watch to wear for 7 days prior to the overnight study visit while filling out a concurrent sleep diary.

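### The 80% power stated for r = 0.47 with 30 participants is about 77% when both variables are measured; 80% power corresponds to r = 0.485, for one marker and 30 complete pairs

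*Combined protocol and SAP*

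**What the plan says.** In the Data Analysis Plan, the Aim 3 power calculation reads: "A sample size of 30 participants will provide 80% power to detect a correlation coefficient equal to 0.47", with a two-sided alpha of 0.05. It names no formula or software, and it does not say whether the predictor is treated as fixed or random. The same paragraph calls the study a pilot whose effect-size information will be useful even if the null hypothesis is not rejected.

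The analysis this refers to comes later under Aim 3, in the part on circadian phase and IR. The relationship "will be assessed by comparing DLMO and DLMOff to the whole body Matsuda index using correlation and linear models". On the melatonin side, "Each subject will have one DLMO time and one DLMOff time". Melatonin onset or offset is the outcome in every model.

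Two other places bear on the figure. The description of the population sets enrolment at up to 30, so 30 is a maximum. Under Study Design and Research Methods, "Participants will have 3 visits: an initial visit, a screening visit, and an overnight study visit"; the OGTT that yields the Matsuda index belongs to the screening visit, and the saliva profile that yields the melatonin times belongs to the overnight visit.

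**The concern.** Power for a correlation depends on whether the predictor values are chosen by the investigator or arise by sampling. If they are chosen, their spread is known in advance. If they are sampled, the spread varies from one set of 30 participants to the next, and that variation lowers average power at this effect size. Here nobody sets the Matsuda index or the melatonin times, so the second case applies. The stated 80% matches the first.

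This sentence is the plan's only quantitative statement of what 30 participants can detect. The plan also expects the pilot to support funding and the planning of a larger study, so an unnamed and mismatched method could be carried forward.

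The sentence also leaves its scope open. There are two melatonin markers, and a usable pair requires two separate visits to succeed, yet the statement does not say that it covers one marker or that it needs all 30 pairs.

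**Working it through.** **Inputs.** From the Aim 3 power calculation: n = 30, r = 0.47, two-sided alpha 0.05, stated power 80%. From the Aim 3 analysis text: a correlation or simple linear model of one melatonin time with the Matsuda index, both measured. The test is the usual t-test with n − 2 = 28 degrees of freedom and critical value 2.048. The t-test of a slope in a one-predictor linear model is the same test.

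**1. Reproducing the plan's figure (predictor fixed).** The t statistic is noncentral t with 28 df and noncentrality

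δ = r/√(1 − r²) × √n = 0.47/√(1 − 0.2209) × √30 = 0.5325 × 5.477 = 2.916.

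Power = P(|T| > 2.048) = **80.4%**. Solving for 80% gives r = 0.468. The stated figure is therefore recovered. With √(n − 1) in place of √n, the same kind of formula gives 79.0%.

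**2. Both variables measured (exact, bivariate normal).** Given the predictor values, T is noncentral t with 28 df and noncentrality 0.5325 × √W, where W is the standardised sum of squares of the predictor about its mean. Over repeated samples W follows a chi-squared distribution with n − 1 = 29 df. Averaging the power over W gives **76.9%**. A simulation of 400,000 bivariate-normal samples of size 30 also gives 76.9%.

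**3. Cross-check by Fisher z.** atanh(0.47) × √(n − 3) = 0.5101 × 5.196 = 2.650. Power ≈ Φ(2.650 − 1.960) = Φ(0.690) = **75.5%**.

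**4. Correlation detectable with 80% power at n = 30.**

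| Method | Power at r = 0.47 | r for 80% power |
|---|---|---|
| Fixed predictor | 80.4% | 0.468 |
| Exact, both measured | 76.9% | 0.485 |
| Fisher z, both measured | 75.5% | 0.492 |

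**5. Could rounding or sidedness explain the difference?** For r between 0.465 and 0.475, exact power runs from 75.9% to 78.0%, so no value that rounds to 0.47 reaches 80%. A one-sided test at 0.05 would give 85.5% (exact), so sidedness does not account for 80% either.

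**6. Number of pairs.** On the exact method r = 0.47 needs 33 pairs: 32 give 79.7% and 33 give 81.0%. The documents give no loss rate. For illustration only, with an assumed number of usable pairs:

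| Usable pairs | Exact power at r = 0.47 | Fixed predictor |
|---|---|---|
| 30 | 76.9% | 80.4% |
| 29 | 75.4% | 78.9% |
| 28 | 73.8% | 77.4% |
| 27 | 72.2% | 75.8% |

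Even on the fixed-predictor formula, the loss of one pair takes power below 80%.

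**The case against.** The strongest reply is that 80% follows from a standard formula, and that the plan lists linear models, where conditioning on the predictor is customary. Conditioning is indeed valid for carrying out the test. It does not settle planning power, because the Matsuda values to be conditioned on do not exist yet and their spread has to be averaged over. What stands is that this is a choice of power model and not a miscalculation.

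A second reply is that 0.485 looks more precise than its assumption allows. The plan itself expects that some variables may be non-normal and may be transformed. In simulations with 30 pairs, r = 0.47 and normal errors, power was 77.9% for a uniform predictor, 76.9% for a normal one, and 75.6%, 73.1% and 68.9% for lognormal predictors with log-scale SD 0.3, 0.5 and 0.7. That 9-point spread is wider than the 3-point gap. The shapes are assumptions, however, and none of them reaches 80%. The point supports naming the bivariate-normal assumption, not keeping the stated figure.

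Third, this is a pilot, 0.47 is not tied to a clinically chosen effect, and no decision turns on 77% against 80%. That is correct and limits the weight of the point.

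Finally, the sentence speaks of a single correlation coefficient and is conditional on 30 participants, so one marker and complete data are the natural reading. That is fair. These two conditions are details worth stating, not errors, and the reduced-pair figures rest on assumed losses.

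**Conclusion.** The concern holds. For one melatonin marker and 30 complete pairs, at two-sided alpha 0.05 and under bivariate normality, power at r = 0.47 is 76.9% instead of 80%, and 80% power corresponds to r = 0.485. The stated figure arises only if the predictor is treated as fixed by design, which does not describe this study. The gap is small, about 3 points of power or 0.015 in detectable correlation, and it does not undermine a pilot that already says it may not reject the null hypothesis. The sentence should still be corrected, because it claims power that the design does not have. The missing scope (one marker, all 30 pairs usable) is a secondary matter of completeness.

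**What to change.** Replace the power sentence in the Aim 3 power calculation with wording such as:

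> Thirty participants with complete data give 80% power to detect r = 0.485 (77% power at r = 0.47) for a single correlation of one melatonin marker with the Matsuda index, two-sided alpha 0.05, exact bivariate-normal method. The figure covers one marker at a time and assumes that all 30 participants, the enrolment ceiling, yield a usable pair.

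If the investigators expect fewer usable pairs, they should give the figure for that number; an assumed 27, for example, gives about 72% at r = 0.47.

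The change is to wording only. No extra enrolment is needed, and procedures and analysis stay as they are. The cost is that the stated figure becomes slightly less favourable.

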## Research Methods

### Outcome Measure(s):

Primary Outcomes: Melatonin phase assessment and IR

Melatonin phase assessment: During the study visit, subjects will be admitted to the Children's Hospital Clinical research center inpatient unit at 4PM on Wednesday, Thursday or Friday. The profile of melatonin release will be assessed at the study visit using a serial saliva sampling method from 5PM on Thursday or Friday to 12PM the following day. Saliva (~2mL) will be collected in 30 or 60 minute intervals in dim light (<10 lux in the room; ~1.9 lux in the angle of gaze, confirmed by light meter) using polystyrene tubes throughout the night. Individualized melatonin sampling schedules will be determined to optimize calculation of DLMOOn and DLMOOff times by introducing 30 minute sampling at the times at which DLMOOn and DLMOOff are predicted to occur based on actigraphy-reported sleep, wake, and midsleep times.

Assessment of IR: During the screening visit, a 3-hour frequently sampled OGTT will be performed in the outpatient CTRC. The OGTT will take place in the AM, after a fast of at least 10 hours. A 20-gauge iv catheter will be inserted in the antecubital vein for blood sampling. After baseline samples are collected, a 3-hour OGTT with 75 mg dextrose drink will be performed. Glucose and insulin samples will be collected every 30 minutes. In addition, we will assess fasting labs to check for other components of metabolic syndrome including hemoglobin A1C for dysglycemia, ALT/AST for liver inflammation, sex hormone binding globulin as a marker of IR, cholesterol panel, CRP as a marker of inflammation, leptin as a gut hormone known to influence hepatic IR, and adiponectin, thought to influence adipose IR. Additionally, blood pressure will be taken to assess for hypertension and waist/hip ratio will be measured as a marker of metabolic disease.

Additional Measures: Questionnaires assessing additional sleep parameters, mood/behavior, and diet/activity will be completed by participants to identify variables to control for in analyses (e.g. presence of symptoms of sleep-disordered breathing) and/or utilize in exploratory analyses (e.g., relationship between sleep and diet/activity).

- i. The **Morningness/Eveningness Scale for Children**  and the **Munich Chronotype Questionnaire for Children**  will be used to determine chronotype (diurnal preference).

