Teens will follow a self-selected sleep schedule during the pre-study week, but data collection will take place during the academic year to capture participants' typical sleep schedule. Data will not be collected during the week following daylight savings changes or in a week following travel across one or two time zones. Average sleep start and end time, sleep duration, and sleep efficiency will be measured.

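### Does the plan need a rule for a subject whose melatonin has not fallen below 4 pg/mL by the noon sample?

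*Combined protocol and SAP*

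**What the plan says.** The Data Analysis Plan, under Melatonin modeling, states that "The timing of melatonin onset and offset will be computed according to standard procedures that have been validated in adolescents". Onset is the interpolated time at which evening melatonin rises above 4 pg/mL and stays there. For offset, "we will define DLMOff phase as the clock time at which salivary melatonin concentrations fall below this threshold", introduced as the parallel of the onset rule. The Aim 3 text on circadian phase and IR then says "Each subject will have one DLMO time and one DLMOff time" and makes onset or offset the outcome of every model that relates melatonin phase to the Matsuda index.

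Under Outcome Measure(s), the melatonin profile is assessed "using a serial saliva sampling method from 5PM on Thursday or Friday to 12PM the following day". The section on the overnight stay repeats the window: "Saliva will be collected every 30-60 minutes from 5pm-noon". Sampling is at 30-minute intervals around the times at which onset and offset "are predicted to occur based on actigraphy-reported sleep, wake, and midsleep times". The exclusion criteria remove "teens not enrolled in a traditional high school academic program", and the Study Design section says that "data collection will take place during the academic year".

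The Aim 1 analysis plan also has variables checked for unusual values and missing data before analysis. Aim 1 itself is to establish a method for measuring and modelling the melatonin profile, onset and offset included.

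**The concern.** An offset defined by a fall below a threshold exists only if the fall is seen. The window closes at noon for everyone; individual schedules change how densely samples are taken, not when sampling ends. A subject at or above 4 pg/mL at the last sample therefore has no DLMOff under the stated definition, yet Aim 3 counts on one from each subject. No section says whether that subject is dropped, set to noon or treated as censored. Checking for missing data is not a rule for handling it.

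The loss would not be random. The missing value would be the latest offset in the sample, and the hypothesis is about delayed offset. Melatonin phase is a primary outcome, enrolment is capped at 30, and the power statement uses all 30. Selecting on the outcome flattens the slope and weakens the correlation, and the pilot's effect sizes are meant to help plan a larger study.

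**Working it through.** **1. The plan's own power figure.** Inputs from the Aim 3 power calculation: n = 30, r = 0.47, two-sided alpha 0.05. With the predictor treated as fixed, the noncentrality is √n · r / √(1 − r²) = 5.477 × 0.47 / 0.8827 = 2.92 on 28 degrees of freedom. This gives power 0.804, so the stated 80% is reproduced. With both variables random, simulation gives 0.77, and the Fisher z approximation gives Φ(0.5101 × √27 − 1.960) = Φ(0.69) = 0.755. The comparisons below are simulated with both variables random, so their baseline is 77% to 78%.

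**2. Effect when the case occurs.** The documents give no frequency, so the first calculation is conditional on a count. Matsuda index and DLMOff are taken as bivariate normal with correlation 0.47 in absolute value and n = 30. Exactly k offsets lie above a cut at the 1 − k/30 quantile; 60,000 pilots were simulated for each k.

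| | k = 1 | k = 2 | k = 3 |
|---|---|---|---|
| Mean r, complete data | 0.467 | 0.466 | 0.467 |
| Mean r, kept at last sample time | 0.465 | 0.462 | 0.460 |
| Mean r, dropped | 0.436 | 0.418 | 0.403 |
| Power, complete data | 77.8% | 78.0% | 77.9% |
| Power, kept | 77.4% | 77.1% | 76.4% |
| Power, dropped | 69.2% | 63.7% | 58.4% |
| Mean slope, complete data | 0.475 | 0.475 | 0.476 |
| Mean slope, kept | 0.459 | 0.443 | 0.428 |
| Significance differs, kept against dropped | 11.5% | 16.7% | 20.9% |
| Significance differs, complete data against k random losses | 4.0% | 6.7% | 8.8% |

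Keeping the subject at the last sample time leaves r and power almost untouched. Its cost is in the slope: 0.459/0.475 = 0.97, 0.443/0.475 = 0.93 and 0.428/0.476 = 0.90, so it shrinks by about 3%, 7% and 10%, roughly the fraction flagged.

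**3. How often the choice could matter.** At an assumed per-subject rate p, the chance of at least one unreached offset among 30 is 1 − (1 − p)^30. For p = 0, 1%, 2% and 5% this is 0, 26%, 45% and 79%. Over all pilots, the significance verdict differs between keeping and dropping in 0, 4%, 6% and 13%. In 200,000 simulated pilots at each of the three non-zero rates, type I error was 5.0% when such subjects were kept and 5.0% to 5.1% when dropped. This is expected: if the two variables are independent, cutting or selecting on one leaves them independent.

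**4. Scale against the pilot's own uncertainty.** For one unreached subject, dropping instead of keeping lowers mean r by 0.465 − 0.436 = 0.029. The standard deviation of r from one pilot is 0.145, five times as large. For planning, n = ((1.960 + 0.842)/atanh(r))² + 3 gives 34.0, 34.4 and 34.8 at the mean r when kept, and 39.0, 42.6 and 46.0 when dropped, a difference of 5 to 11 subjects. At one standard deviation either side of 0.467 (r = 0.612 and 0.322), the same formula gives about 18 and 73.

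**The case for a change.** The strongest contrary case is that keeping or dropping is a free choice until it is written down, and that it changes the significance verdict in 11% to 21% of pilots with one to three unreached offsets, more than twice the effect of losing as many subjects at random. A rule would take one sentence and no extra samples. If unreached offsets were common, dropping would be serious: at assumed shares of 10%, 20% and 30%, power falls to 58%, 45% and 35%, against 76%, 74% and 71% with those subjects set to noon.

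Part of this stands. No section states the rule, and dropping would be the worse choice. But no section says that such subjects would be dropped, and the documents give no support for shares of that size, or for any case at all. They point the other way: a 19-hour window, sampling concentrated around the predicted offset, pupils on a school timetable and collection in term time. The cited procedures may already cover the case; their content cannot be checked from the documents. The effect on planning is real on average but small beside the uncertainty of a single r from 30 subjects.

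**Conclusion.** No change to the plan is needed. This is a gap in wording that an analyst would fill sensibly: follow the cited procedures if they have a rule; otherwise enter the last sample time, flag the value as censored and report how many there are. So handled, one to three such subjects move mean r by at most 0.007 and power by at most 1.5 percentage points, and shrink the DLMOff slope by 3% to 10%. The analysis of DLMO is untouched, and type I error stays at about 5%. Finding out how awkward profiles behave is also part of what Aim 1 sets out to do.

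The conclusion rests on bivariate normal data with a correlation of 0.47, on unreached offsets being few, and on their not being discarded. The true frequency is unknown and may be nil. The larger losses above require both an assumed frequency and a decision to drop such subjects, and the plan contains neither.
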